17.3. ECG EVALUATIONS

Results from the central Electrocardiogram (ECG) Reading Centre will be included in the

[REDACTED]

reporting of this study. ECG evaluations will be presented separately for 24-week and 48-week strata.

The following ECG parameters will be reported for this study:

- PR Interval (msec)
- QRS Interval (msec)
- QT Interval (msec)
- QTcF Interval (msec)
- QTcB Interval (msec)
- Heart Rate (beats per minute [bpm])
- Overall assessment of ECG (Investigator's judgment):
 - Normal
 - Abnormal, Not Clinically Significant (ANCS)
 - Abnormal, Clinically Significant (ACS)

On Day 1, prior to dosing, triplicate ECGs must be performed. Triplicate results will be used in the summaries by taking an average of the 3 results. The average of the 3 results will be the baseline. Baseline for the investigator's judgement will be the mode judgment of the 3 results. In the case of multiple modes, the mode with the worst-case judgment (Normal<ANCS<ACS) will be used as baseline.

If only 2 ECG measurements instead of triplicate on Day 1 pre-dose, take average of the two; if only 1 measurement then this will be the baseline.

The handling of re-test and unscheduled measurements is detailed in Section 6.3 of the SAP.

If there were more measurements on a scheduled visit, choose measurement as follows:

1. Choose first triplicate, if more than one done.
2. If done on Day 1, ensure you choose measurement that it is prior to dosing.
3. If there are more than 1 ECG measurements, choose the scheduled one where interpretation of the measurement from the vendor data is not "UNABLE TO EVALUATE" .
 - a. If pre-dose/post-dose and interpretation of the measurement from the vendor data is "UNABLE TO EVALUATE" and no further pre-dose/post-dose unscheduled visits on the same day, respectively – set to missing
 - b. If pre-dose/post-dose and interpretation of the measurement from the vendor data is "UNABLE TO EVALUATE" and there is another unscheduled pre-dose/post-dose – choose next unscheduled visit on the same day

[REDACTED]

The following summaries will be provided for ECG data:

- Actual and change from baseline by visit (for quantitative measurements)
- Shift table representing changes from Normal, ANCS and ACS, using Investigator's judgement
- Incidence of markedly abnormal criteria
- Listing of patients meeting markedly abnormal criteria

17.3.1. ECG MARKEDLY ABNORMAL CRITERIA

Markedly abnormal quantitative ECG measurements will be identified in accordance with the following predefined markedly abnormal criteria:

- Absolute values for QT interval, QTcB interval and QTcF interval will be classified as:
 - > 450 msec
 - > 480 msec
 - > 500 msec
- Change from Baseline for QT interval, QTcB interval and QTcF will be classified as:
 - >30 msec increase from baseline
 - >60 msec increase from baseline

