2.3 Benefit/Risk Assessment

No significant medical risks to patients have been identified from studies conducted thus far with ensifentrine administered in the solution formulation, suspension formulation, or dry powder formulation. A slight increase in mean heart rate (up to 12 beats per minute [bpm]) without reported medical significance at a 6 mg supratherapeutic doses has been reported in healthy volunteers (RPL554-PK-101). In patients with COPD, transient increases in peak heart rate of 3 bpm vs placebo have been observed with the 6 mg twice daily dose only over 4 weeks. Otherwise, non-clinical and clinical data to date do not indicate any areas of particular medical safety concern.

Effects on reproductive performance in male rats given the highest dose of 15.5 mg/kg/day included lower number of pairings of dosed males resulting in pregnancy in undosed females, higher pre and post implantation loss resulting in lower mean litter size, and lower sperm motility and higher abnormal sperm. No ensifentrine-related adverse effects were observed at 5.75 mg/kg/day (20.5 times the maximum recommended human dose based on area under the curve [AUC]). There were no effects on embryo-fetal survival and development in either rats or rabbits in the main embryo-fetal development studies. Ensifentrine had no effects on fertility or reproductive performance in female rats.

Ensifentrine has statistically and clinically significant bronchodilator as well as anti-inflammatory effects. As such, the clinical development of ensifentrine is focused on the treatment of obstructive and inflammatory lung diseases, including COPD.

Considering the consistent improvements in lung function, symptoms, and health-related quality of life across multiple studies in patients with COPD and the overall favorable safety profile in studies to date, the benefit/risk profile of ensifentrine is considered positive.

More detailed information about the known and expected benefits and risks and reasonably expected AEs of ensifentrine can be found in the Verona Pharma plc. Ensifentrine Clinical IB v. 20.0, 2021 (or more current version, if applicable).

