8.4.1 Vital Signs

- Vital signs should be obtained prior to blinded study medication dosing at all visits.
- Temperature in Celsius, pulse rate, blood pressure, and respiratory rate will be assessed. The mode of temperature collection should be noted in the source (e.g. oral, forehead, etc).
- Blood pressure and pulse measurements will be assessed with a completely automated device. Manual techniques will be used only if an automated device is not available.
- Supine blood pressure, respiratory rate, and pulse measurements should be obtained after the patient has been at rest for at least 5 minutes in the supine position and located in a quiet setting without distractions (eg, television, cell phones).

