9.4.2 Safety Analyses

Safety analysis will be based on the safety set.

Adverse events will be analyzed using quantitative and qualitative measures. Treatment-emergent adverse events will be summarized by treatment group for all AEs, related AEs, serious adverse events, deaths, adverse events leading to discontinuation of blinded study medication or to withdrawal from study, adverse events of different severity and adverse events of different chronicity. Treatment-emergent adverse events will be coded using the Medical Dictionary for Regulatory Activities (MedDRA) and summarized by system organ class and preferred term for each treatment group. For selected adverse events, time to first event will be visualized using Kaplan-Meier plots.

Laboratory data will be summarized by each visit including change from baseline. The number of normal, abnormal not clinically significant and abnormal clinically significant values on each parameter will be summarized for change over study using shift tables. All data will be listed and values outside reference ranges will be highlighted in the listings.

Vital signs and continuous parameters from the ECGs will be summarized by each visit including change from baseline. Values outside pre-specified ranges (low, high) or changes exceeding pre-specified limits will be summarized by visit for each parameter. The number of normal, abnormal not clinically significant and abnormal clinically significant values on the ECG overall evaluation will be summarized for change over study using shift tables. All data will be listed and values outside reference ranges will be highlighted in the listings.

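### SAP 17.3.1 sets no limit for ECG heart rate, so patients who exceed a rate threshold after dosing are not counted by arm

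*SAP*

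**What the plan says.** SAP 17.3 names heart rate among the ECG parameters, beside PR, QRS and the QT measures. It plans by-visit values and changes, a shift table of the investigator's overall judgement, an incidence table and a listing of markedly abnormal findings.

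The criteria behind the incidence table and listing are in 17.3.1. They cover absolute values ("Absolute values for QT interval, QTcB interval and QTcF interval will be classified as" above 450, 480 or 500 msec) and increases ("Change from Baseline for QT interval, QTcB interval and QTcF will be classified as" above 30 or 60 msec). Heart rate does not appear; nor do PR and QRS.

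Rate limits appear only in SAP 17.4.1, for pulse: 50 bpm or lower, 110 bpm or higher, or a change of at least 30 bpm in either direction. Protocol 8.4.1 fixes the timing of pulse: "Vital signs should be obtained prior to blinded study medication dosing at all visits".

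Protocol 9.4.2, on vital signs and continuous ECG parameters, says: "Values outside pre-specified ranges (low, high) or changes exceeding pre-specified limits will be summarized by visit for each parameter". SAP 3.3, which lists changes from the protocol's analysis, does not mention the matter.

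**The concern.** Heart rate is the one ECG or vital-sign change that the protocol describes for this drug. Protocol 2.3 reports a mean rise of up to 12 bpm at 6 mg in healthy volunteers. In COPD, "transient increases in peak heart rate of 3 bpm vs placebo have been observed with the 6 mg twice daily dose only". Protocol 4.3 repeats the COPD finding as the single exception to an otherwise unchanged ECG and vital-sign profile.

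The effect is described as transient. After Day 1, pre-dose pulse is a trough value, roughly 12 hours after the previous evening's dose. The plan therefore applies its rate limits where a transient effect is least likely to show, and applies none at the post-dose ECG. What is lost is a simple descriptive count: how many patients in each arm had a post-dose heart rate, or a rise, beyond a stated limit.

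**Working it through.** **Passages side by side**

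| Measurement | Timing | Limits in the SAP | Count by arm against a limit |
|---|---|---|---|
| Pulse (vital signs) | Before dosing (Protocol 8.4.1) | ≤50, ≥110, change ≥30 bpm (17.4.1) | Yes |
| ECG QT, QTcB, QTcF | Pre-dose and 1.5 h post-dose (Protocol 1.3) | >450, >480, >500 msec; increase >30, >60 msec (17.3.1) | Yes |
| ECG heart rate | Pre-dose and 1.5 h post-dose (Protocol 1.3) | None | No |

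Protocol 11.5 does contain ECG heart-rate levels, among them sinus tachycardia at 120 bpm or more and an increase of 40 bpm or more. It uses them as withdrawal criteria, and the SAP does not tabulate them.

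**What a mean can and cannot show**

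The plan gives no figure to reproduce here, so this is an illustration.

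Inputs from the documents:
- 500 vs 300 patients overall (Protocol 9.2).
- About 400 patients randomized 1:1 for 24 weeks, hence 200 vs 200, and about 400 randomized 3:1 for 48 weeks, hence 300 vs 100 (Protocol 1.1). SAP 17.3 presents ECG data separately for these two strata.
- A rise of 30 bpm, the pulse change limit in SAP 17.4.1.

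Assumptions, because the documents give no figures:
- 2% of ensifentrine patients rise by 30 bpm at 1.5 h, and nobody else changes on average.
- The SD of heart-rate change is 8 to 12 bpm.

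Shift in the ensifentrine mean = 0.02 × 30 = 0.6 bpm, overall and in each stratum.

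Standard error of the arm difference = SD × √(1/n₁ + 1/n₂):
- Overall: 8 × √(1/500 + 1/300) = 0.58 and 12 × √(1/500 + 1/300) = 0.88 bpm.
- 24-week stratum: 8 × √(2/200) = 0.80 and 12 × √(2/200) = 1.20 bpm.
- 48-week stratum: 8 × √(1/300 + 1/100) = 0.92 and 12 × √(1/300 + 1/100) = 1.39 bpm.

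The shift is about one standard error at most overall and less than one in either stratum, so a table of means would not reliably show it. A count would read 4 of 200, 6 of 300 and 10 of 500 in the ensifentrine arms. With a 40 bpm rise in 0.5%, 1% or 2% of 500 patients (2.5, 5 or 10 patients expected), the mean shift is 0.2, 0.4 or 0.8 bpm.

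**The case against.** The best reply is that such patients have other ways to surface, and much of it stands.

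- **Extremes are printed.** SAP 6.5 makes minimum and maximum default statistics, so the largest rise by arm and visit should be visible. It does not say whether one patient or ten were affected.
- **Non-specific tables exist.** The ECG shift table ("Shift table representing changes from Normal, ANCS and ACS") can reflect tachycardia. A finding judged clinically significant is an adverse event and enters the TEAE tables. Discontinuations are tabulated, and Protocol 9.4.2 promises full listings with out-of-range values highlighted.
- **QTcB moves with rate.** From the two correction formulas, QTcB = QTcF × (HR/60)^(1/6). With QTcF held at an assumed 420 msec, a rise from 75 to 105 bpm takes QTcB from 436 to 461 msec, past the 450 msec criterion. That would flag the patient, but not for heart rate.

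A reader might therefore infer that post-dose tachycardia would be missing from every planned table. The documents do not support that: what is missing is incidence by arm against a pre-specified heart-rate limit.

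Three other strong readings also fail:

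- **That the drug raises heart rate at the study dose.** Both described effects are at 6 mg. Protocol 4.3 reports no ECG or vital-sign change in COPD patients at other doses.
- **That the SAP plainly breaches Protocol 9.4.2.** The sentence can be read as covering only parameters for which limits are later set. Temperature and respiratory rate have no limits either. It is an unexplained difference, not a proven breach.
- **That a significant difference between arms would be lost.** SAP 17 plans no statistical comparisons for safety data unless specified, and ECG data are split by stratum. The gap concerns what is visible, not a test.

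The output shells are not among the documents and may hold more detail, but the SAP text defines no heart-rate limit for a shell to apply.

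**Conclusion.** The point holds in this limited form. The SAP text plans no count of patients beyond a heart-rate limit at the only scheduled post-dose rate measurement, while it does so for pre-dose pulse and for post-dose QT. Protocol 9.4.2 gives reason to expect such a summary, and the SAP neither provides it nor explains its absence.

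The size is small. No heart-rate effect is described at 3 mg, and several planned outputs could reveal individual cases. The conclusion that means alone are a weak detector rests on the assumed 2% frequency, 30 bpm rise and SD of 8 to 12 bpm. The gap itself rests on the text alone. PR and QRS also lack limits; heart rate is singled out because it is the one change that the protocol describes. The change is worth making because it costs almost nothing.

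**What to change.** In SAP 17.3.1, add categories for ECG heart rate at pre-dose and at 1.5 h post-dose, for tabulation only. Take the limits from the documents, so that none is chosen after seeing data: the pulse limits of 17.4.1 (≤50, ≥110, change ≥30 bpm) and the Protocol 11.5 levels of ≥120 bpm and an increase ≥40 bpm. This has no bearing on the withdrawal rules.

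Carry the categories into the incidence table, the listing and the Extended Safety Set run in 17.7. Show them pooled as well as by stratum. Add a note to 17.4.1 that pulse values are pre-dose. If the sponsor prefers not to add the rows, it should record the departure from Protocol 9.4.2, with a reason, in SAP 3.3.

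The cost is a few lines of SAP text, extra rows in an existing table and one pooled display. The ECG data are already collected.

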17.4. VITAL SIGNS

The following Vital Signs measurements will be reported for this study:

- Supine Systolic Blood Pressure (mmHg)
- Supine Diastolic Blood Pressure (mmHg)
- Supine Pulse Rate (bpm)
- Respiratory Rate (breaths/min)
- Temperature ($^{\circ}$ C)
- Body weight (kg)
- Height (cm)
- BMI (kg/m^2)

Vital signs will be presented separately for 24-week and 48-week strata. The following summaries will be provided for vital signs data (excluding respiratory rate, temperature, body weight, height and BMI):

- Actual and change from baseline by visit
- Incidence of markedly abnormal values

- Shift from baseline according to markedly abnormal criteria
- Listing of patients meeting markedly abnormal criteria

Respiratory rate, temperature, body weight, height and BMI will be listed.

17.4.1. VITAL SIGNS MARKEDLY ABNORMAL CRITERIA

Markedly abnormal quantitative Vital Signs measurements will be identified in accordance with the predefined markedly abnormal criteria found in Table 5.

Markedly Abnormal Post-Baseline Vital Signs

Variable	Unit	Abnormally Low	Abnormally High
SBP	mmHg	- A decrease from Baseline of ≥ 40 - Value ≤ 90	- An increase from Baseline of ≥ 40 - Value ≥ 180
DBP	mmHg	- A decrease from Baseline of ≥ 20 - Value ≤ 50	- An increase from Baseline of ≥ 20 - Value ≥ 105
Pulse rate	Bpm	- A decrease from Baseline of ≥ 30 - Value ≤ 50	- An increase from Baseline of ≥ 30 - Value ≥ 110

17.5. COVID-19

From study initiation until 5Nov2021, patients with positive COVID-19 test indicating an active COVID-19 infection were withdrawn from the study.

A protocol clarification letter dated 5Nov2021 clarified that active infection includes known symptoms of COVID-19.

A protocol clarification letter dated 21Apr2022 clarified that active infection includes known lower respiratory symptoms of COVID-19.

Patients who discontinued due to COVID-19 will be summarized in the disposition table. Data collected on the "COVID-19 Visit Impact" eCRF page will be summarized by visit. Data on the optional COVID-19 testing will be listed.

17.6. PNEUMONIA

Pneumonia details recorded in the “Pneumonia” page of the eCRF will be listed.

17.7. EVALUATION INCLUDING EXCLUDED SITES

The following analyses will be performed on the Extended Safety Set:

- Summary of TEAEs
- TEAEs by SOC and PT
- Related TEAEs by SOC and PT
- Serious TEAEs by SOC and PT
- Markedly abnormal values for selected chemistry parameters
- Markedly abnormal values for vital signs
- Markedly abnormal values for ECG parameters

18. DATA NOT SUMMARIZED OR PRESENTED

The other variables and/or domains not summarized or presented are:

- Comments
- Physical Examinations, as it is not collected within eCRF

These domains and/or variables will not be summarized or presented, but if collected will be available in the clinical study database, SDTM and/or ADaM datasets.

[REDACTED]

APPENDIX 1. PROGRAMMING CONVENTIONS FOR OUTPUTS

DATES & TIMES

Depending on data available, dates and times will take the form yyyy-mm-ddThh:mm:ss.

SPELLING FORMAT

English US.

PRESENTATION OF TREATMENT GROUPS

For outputs, treatment groups will be represented as follows and in the given order:

Treatment Group	For Tables, Listings and Graphs
Ensifentrine	Ensifentrine
Placebo	Placebo
Not Randomized	Not Randomized

DECIMAL PLACES

The decimal places for this study will use the following rules, unless otherwise stated.

Value = x dp

Mean = x+1 dp

Standard Deviation = x+2 dp

Median = x+1 dp

Q1/Q3 = x+1 dp

Minimum/Maximum = x dp

CI = x+1 dp

In case a variable has values with infinite decimal places, the following rules will be used:

Value = 1 dp

Mean = 2 dp

Standard Deviation = 3 dp

Median = 2 dp

Q1/Q3 = 2 dp

Minimum/Maximum = 1 dp

CI = 2 dp

For spirometry data we will present outputs with decimal places for value as follows:

- Values in liters = 3 dp, i.e. mean/median/Q1/Q3/CI in liters = 4 dp, standard deviation = 5 dp and minimum/maximum = 3 dp.
- Values in milliliters = 0 dp, i.e. mean/median/Q1/Q3/CI in liters = 1 dp, standard deviation = 2 dp and minimum/maximum = 0 dp.
- Percentage values = 1 dp, i.e. mean/median/Q1/Q3/CI in liters = 2 dp, standard deviation = 3 dp and minimum/maximum = 1 dp.

P-values will be presented to 4dp.

PRESENTATION OF VISITS

For outputs, visits will be represented as follows and in that order:

Long Name (default)	Short Name
Screening	Screening
day 1	day 1
week 6	week 6
week 12	week 12
week 18	week 18
week 24	week 24
week 30	week 30
week 36	week 36
week 42	week 42
week 48	week 48
Follow-up	Follow-up

LISTINGS

All listings will be ordered by the following (unless otherwise indicated in the template):

[REDACTED]	[REDACTED]	[REDACTED]	[REDACTED]
[REDACTED]	[REDACTED]	[REDACTED]	[REDACTED]
[REDACTED]	[REDACTED]	[REDACTED]	[REDACTED]
[REDACTED]	[REDACTED]	[REDACTED]	[REDACTED]
[REDACTED]	[REDACTED]	[REDACTED]	[REDACTED]

- Randomized treatment group (or treatment received if it's a safety output), first by active dose and then placebo,
- Center-patient ID,
- Date and time (where applicable),
- For listings where non-randomized patients are included, these will appear in a category after the randomized treatment groups labeled 'Not Randomized'.

TABLES

All tables presenting multiple events that map to a SOC and PT will be counted only once, per unique patient, for incidence counts. Events will be presented in descending frequency of SOC and PT (unless otherwise indicated in the shells).

[REDACTED]	[REDACTED]	[REDACTED]	[REDACTED]
[REDACTED]	[REDACTED]	[REDACTED]	[REDACTED]
[REDACTED]	[REDACTED]	[REDACTED]	[REDACTED]
[REDACTED]	[REDACTED]	[REDACTED]	[REDACTED]

APPENDIX 2. PARTIAL DATE CONVENTIONS

Imputed dates will NOT be presented in the listings.

ALGORITHM FOR TREATMENT EMERGENCE OF ADVERSE EVENTS:

START DATE	STOP DATE	ACTION
Known	Known/Partial/ Missing	If start date < study med start date, then not TEAE If start date >= study med start date, then TEAE
Partial, but known components show that it cannot be on or after study med start date	Known/Partial/ Missing	Not TEAE
Partial, could be on or after study med start date OR Missing	Known	If stop date < study med start date, then not TEAE If stop date >= study med start date, then TEAE
	Partial	Impute stop date as latest possible date (i.e. last day of month if day unknown or 31st December if day and month are unknown), then: If stop date < study med start date, then not TEAE If stop date >= study med start date, then TEAE
	Missing	Assumed TEAE

**ALGORITHM FOR PRIOR/ PRIOR CONCOMITANT / CONCOMITANT MEDICATIONS:**

START DATE	STOP DATE	ACTION
Known	Known	
If stop date < study med start date, assign as prior
 
If stop date >= study med start date and start date < study med start, assign as prior concomitant
 
If stop date >= study med start date and (start date > study med start or start date <= end of treatment), assign as concomitant
 
If start date > end of treatment, assign as post study

	Partial	
Impute stop date as latest possible date (i.e. last day of month if day unknown or 31st December if day and month are unknown), then:
 
If stop date < study med start date, assign as prior
 
If stop date >= study med start date and start date < study med start, assign as prior concomitant
 
If stop date >= study med start date and (start date > study med start or start date <= end of treatment), assign as concomitant
 
If start date > end of treatment, assign as post study

	Missing	
If stop date is missing could never be assumed a prior medication
 
If stop date >= study med start date and start date < study med start, assign as prior concomitant
 
If stop date >= study med start date and (start date > study med start or start date <= end of treatment), assign as concomitant
 
If start date > end of treatment, assign as post study

START DATE	STOP DATE	ACTION
Partial	Known	Impute start date as earliest possible date (i.e. first day of month if day unknown or 1st January if day and month are unknown), then: If stop date < study med start date, assign as prior If stop date >= study med start date and start date < study med start, assign as prior concomitant If stop date >= study med start date and (start date > study med start or start date <= end of treatment), assign as concomitant If start date > end of treatment, assign as post study
	Partial	Impute start date as earliest possible date (i.e. first day of month if day unknown or 1st January if day and month are unknown) and impute stop date as latest possible date (i.e. last day of month if day unknown or 31st December if day and month are unknown), then: If stop date < study med start date, assign as prior If stop date >= study med start date and start date < study med start, assign as prior concomitant If stop date >= study med start date and (start date > study med start or start date <= end of treatment), assign as concomitant If start date > end of treatment, assign as post study
	Missing	Impute start date as earliest possible date (i.e. first day of month if day unknown or 1st January if day and month are unknown), then: If stop date is missing could never be assumed a prior medication If stop date >= study med start date and start date < study med start, assign as prior concomitant If stop date >= study med start date and (start date > study med start or start date <= end of treatment), assign as concomitant If start date > end of treatment, assign as post study

[REDACTED]
[REDACTED]
[REDACTED]
[REDACTED]
[REDACTED]
[REDACTED]
[REDACTED]
[REDACTED]
[REDACTED]
[REDACTED]

START DATE	STOP DATE	ACTION
Missing	Known	If stop date < study med start date, assign as prior If stop date >= study med start date, assign as concomitant Cannot be assigned as 'prior concomitant' and 'post treatment'
	Partial	Impute stop date as latest possible date (i.e. last day of month if day unknown or 31st December if day and month are unknown), then: If stop date < study med start date, assign as prior If stop date >= study med start date, assign as concomitant Cannot be assigned as 'prior concomitant' and 'post treatment'
	Missing	Assign as concomitant

[REDACTED]

[REDACTED]

[REDACTED]

[REDACTED]

[REDACTED]

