9.4.3 Other Analyses

The patient flow including total number of screened patients, number of randomized patients, completers, withdrawn patients (including reason for withdrawal) and patients included in each of the analysis sets will be summarized by treatment group and for the total.

The number of patients with major protocol deviations will be summarized by category of violation and by treatment group including subset of major protocol deviation leading to exclusion from the per-protocol set.

Demographic and baseline characteristics will be summarized using descriptive statistics for each treatment group and for the total number of randomized patients. Medical history will be coded using MedDRA and summarized by system organ class and preferred term for each treatment group. Prior medications will denote medications used prior to first dose of study drug independent of if stopped at randomization or not. Concomitant medications will denote medications started prior to but continuing after randomization or medications with a start date at or after the randomization date. Prior and concomitant medications will be summarized separately by Anatomical Therapeutic Chemical (ATC) levels 2 and 4.

Compliance to blinded study medication will be computed based on the number of ampules/foil pouch count dispensed and returned. Non-compliance will be defined as a compliance value less than 70% over the full study period. Secondly, compliance will also be computed based on recording of study drug intake in the diary.

The impact of COVID-19 on the study participation of all patients will be captured on a separate eCRF page and include items such as attendance at in-clinic study visits. Details of presentation will be outlined in the Statistical Analysis Plan.

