15. SABA/ICS
16. SABA/ Corticosteroid
17. Short-Acting Anti-Muscarinic

See Appendix 2 for handling of partial dates for medications, in the case where it is not possible to define a medication as prior, concomitant, or post treatment, the medication will be classified by the worst case; i.e. concomitant.

- ‘Prior’ medications are medications which started prior to the first dose of study medication and stopped prior to the first dose of study medication.
- ‘Prior Concomitant’ medications are medications which started prior to the first dose of study medication and ended on or after the date of first dose of study medication or were ongoing at the end of the study.
- ‘Concomitant’ medications are medications which:
 - started on or after the first dose of study medication and started no later than last day of study medication intake,
 - AND ended on or after the date of first dose of study medication or were ongoing at the end of the study.
- ‘Post’ medications are medications which started from the day after the last dose of study medication.

Prior, prior concomitant and concomitant COPD medications will be presented separately for the SAF set. COPD medications are those provided by medical review and will be presented as preferred term and ATC levels 1, 2 and 4.

Data captured on the “Concomitant Medications” page of the eCRF will be presented for each treatment group. Patients with multiple medications within an ATC/ therapeutic subgroup will only be counted once for that level.

[REDACTED]	[REDACTED]	[REDACTED]	[REDACTED]
[REDACTED]	[REDACTED]	[REDACTED]	[REDACTED]
[REDACTED]	[REDACTED]	[REDACTED]	[REDACTED]
[REDACTED]	[REDACTED]	[REDACTED]	[REDACTED]

Oxygen therapy and CPAP will be listed separately to other medications. Oxygen therapy is defined by ATC code: “V03AN” and route is not Oral; CPAP is defined by ATC code: “R07AX” and route is not Oral.

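### The concomitant-medication rule in SAP Appendix 2 joins its two start-date limits with 'or', so it is always met, the classes overlap, and the result depends on an unstated rule order

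*SAP*

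**What the plan says.** SAP Section 13 (Medications) sets out four classes. *Prior* means started and stopped before first dose. *Prior concomitant* means started before first dose and ended on or after it, or still ongoing. *Concomitant* means "started on or after the first dose of study medication and started no later than last day of study medication intake", and also ended on or after first dose or ongoing. *Post* means "medications which started from the day after the last dose of study medication". Where the class cannot be determined, "the medication will be classified by the worst case; i.e. concomitant". Section 13 sends the reader to Appendix 2 for partial dates. It presents prior, prior concomitant and concomitant medications separately, and does the same for COPD medications.

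The medication algorithm in SAP Appendix 2 has nine cells, from a known, partial or missing start date crossed with a known, partial or missing stop date. The six cells with a known or partial start date share three rules, in this order:

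- "If stop date >= study med start date and start date < study med start, assign as prior concomitant"
- a rule requiring the stop date to be on or after study med start and then testing a bracket that ends "start date > study med start or start date <= end of treatment), assign as concomitant"
- a last rule, for medications begun once treatment is over: "If start date > end of treatment, assign as post study"

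The known-stop and partial-stop cells open with a rule for *prior*. The missing-stop cells open instead with "If stop date is missing could never be assumed a prior medication", and then still compare the stop date with the start of study medication. The three missing-start cells do not use the bracket.

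Protocol Section 9.4.3 has a simpler definition. Concomitant medications are those continuing past randomization or "medications with a start date at or after the randomization date", with no upper date limit and no post class.

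**The concern.** Section 13 needs both limits and Appendix 2 asks for either. A condition that every date meets cannot separate anything, so the two parts of the SAP give different classes even when all dates are fully known. Section 13's worst-case fallback does not cover this: it is for medications whose class cannot be determined, whereas here a medication with complete dates qualifies for two classes.

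At stake is the content of the by-arm medication tables. Depending on how the rules are coded, either therapy begun after study drug stopped is shown as used during treatment, or therapy carried over from before first dose is merged with newly started therapy. Such records can exist. Patients who stop study drug may stay in the study and have concomitant medication assessed under all three reduced-participation options (Protocol Sections 7.2.1 to 7.2.3), and Section 8.5.1 asks for a query at every contact.

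**Working it through.** The documents give no figure to reproduce on this point; the check is one of logic.

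**Notation.** s = medication start, t = medication stop, S = first dose, E = end of treatment, with S <= E. E is taken to be the last day of study medication intake in Section 13.

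**1. The bracket is always true.** It reads (s > S) or (s <= E). If s > S, the first limb holds. If s <= S, then s <= S <= E and the second holds. This includes the case S = E. The concomitant rule therefore reduces to t >= S.

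**2. The classes overlap.** Take S = day 1 and E = day 169, for illustration only.

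- Start day 180, stop day 190: concomitant (190 >= 1 and 180 > 1) and also post (180 > 169). Section 13 says post.
- Start day -50, stop day 30: prior concomitant (30 >= 1 and -50 < 1) and also concomitant (30 >= 1 and -50 <= 169). Section 13 says prior concomitant.

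**3. Both possible orders.** The Appendix 2 rules were coded literally for every start/stop pair from day -100 to day 299 with stop on or after start: 400 × 401 / 2 = 80,200 pairs. Under Section 13 they divide as follows:

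- prior: 101 × 102 / 2 = 5,151
- prior concomitant: 101 × 299 = 30,199
- concomitant: 169 × 300 - 169 × 170 / 2 = 36,335
- post: 130 × 131 / 2 = 8,515

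| Section 13 class | Pairs | First match wins | Last match wins |
|---|---|---|---|
| Prior | 5,151 | prior | prior |
| Prior concomitant | 30,199 | prior concomitant | **concomitant** |
| Concomitant | 36,335 | concomitant | concomitant |
| Post | 8,515 | **concomitant** | post |

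Each order misplaces one whole class. The counts describe a grid of dates, not patients or records, and say nothing about how common either error would be.

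**4. Missing stop date.** Of the 400 start dates on the grid, 101 fall before first dose, 169 on treatment and 130 after. If a missing stop date simply fails the comparison t >= S, the 130 later starts meet only the post rule and are classed correctly, but the other 270 (101 + 169) receive no class. If a missing stop date counts as ongoing, the overlap of step 2 returns: the 101 meet both prior concomitant and concomitant, and the 130 meet both concomitant and post.

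**5. Candidate repairs.**

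- Changing only 'or' to 'and' removes the overlap, but a medication started exactly on the first-dose day gets no class (299 of 80,200 pairs), because the rule has s > S where Section 13 includes that day.
- With (s >= S and s <= E), all 80,200 pairs match Section 13 under both orders.
- With that bracket and a missing stop date treated as ongoing, each start date meets exactly one rule: s < S is prior concomitant, S <= s <= E is concomitant, s > E is post.

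**The case against.** The best defence is that Section 13 already states the intended rule without ambiguity, with four classes that do not overlap, so a programmer working from the body of the SAP would get it right. That makes this a drafting slip, and it lowers the likely harm. But Appendix 2 is the operative algorithm, its known-start/known-stop cell repeats the bracket, and nothing says which section prevails.

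Second, Protocol Section 6.8 keeps medications begun after the end of study treatment out of the eCRF unless given for a serious adverse event, and it names early termination as one such end. This stands as a limit on numbers. It does not empty the class, given the continued collection in patients who stop drug and stay.

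Third, the protocol's own definition has no upper limit, so classing later starts as concomitant agrees with Protocol Section 9.4.3. That is correct; the contradiction is within the SAP, which created the post class.

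A reader might infer more than the documents support:

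- *That post can never be assigned.* This holds only for medications with a usable stop date, under first match. The post rule is written in all six cells. It survives under last match, and also when a missing stop date fails the comparison.
- *That on-treatment use of prohibited medication would be overstated.* Section 13 plans no prohibited-medication table, and exclusions for such use are settled at the blinded data review (SAP Section 5.7), not by this class.
- *That efficacy results are exposed.* The background-therapy stratum has its own date rule (SAP Section 6.9), and no model or analysis set is shown to use these classes.
- *That the arms would be distorted by a known amount.* The documents give no rate of new therapy after stopping study drug, so no figure can be offered.

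**Conclusion.** The point holds in a limited form. The start-date bracket in six cells of Appendix 2 is met by every date and contradicts Section 13. With a stop date present, post-treatment starts qualify for two classes and so do prior-concomitant medications, and the SAP states no order to decide between them. Neither natural order gives the Section 13 classes, so the descriptive prior concomitant or concomitant tables, including those for COPD medication, would be wrong if coded as written.

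The severity is minor. The effect is descriptive, and Protocol Section 6.8 limits the number of post-treatment records. Any imbalance between arms would depend on discontinuation and later prescribing, which the documents do not quantify. The conclusion assumes only that end of treatment is not before first dose and that it means the last day of study medication intake. The day-169 end of treatment is illustrative; the logic does not depend on it.

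**What to change.** In Appendix 2, for all six cells with a known or partial start date:

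1. Replace the bracket with `(start date >= study med start AND start date <= end of treatment)`. Both changes are needed: 'and' for 'or', and '>=' for '>' at the lower limit.
2. State that the four classes are mutually exclusive.
3. State that a missing stop date is treated as ongoing, that is, as on or after study med start, in these comparisons. This follows Section 13, which includes ongoing medications. It matters for background LAMA or LABA therapy, whose end date is documented as ongoing (Protocol Section 6.7.4.1), if such entries are held without a stop date.

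The cost is a text correction in Appendix 2 and a small change to the classification code. If the tables are already programmed, check whether the code followed Section 13 or Appendix 2. No data collection, efficacy analysis or sample size is touched.
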